9.6. Data Management

This study will use secondary data collected in the PharMetrics Plus database, which is de-identified and HIPAA compliant. The data will be made accessible only to individuals working on the current study. No attempt will be made to identify individual patients, hospitals, or physicians. Analyses will be conducted using Statistical Analysis System (SAS) 9.4 (SAS Institute, Cary, NC).

The analytic files will include person-level data, including information on baseline demographic and clinical characteristics, study outcomes, and vaccination information as described in the variable section above. Data for this study will be processed and managed by Pfizer, Inc., and all analyses will be performed by Pfizer.

9.7. Data Analysis

The zero time is the date of Trumenba vaccination for the exposed group and the date of MenACWY for the unexposed group. We will assess gonococcal infections that occurred between i) 14 days after zero time and 365 days ii) 14 days after zero time and 730 days, iii) 14 days after zero time and 1095 days, and iv) 14 days after zero time and till end of the study period (31Dec2022). We will censor the data in the event of interest, death date (if known), plan disenrollment (if known), target end date, or the end of the study period, whichever comes first. In descriptive analyses, we will fit Kaplan-Meier curves. We will also create unadjusted and covariate adjusted Cox proportional hazard regression models verifying first that the proportionality assumption was satisfied for all independent variables. Hazard ratios (HRs) will be estimated by exponentiation of the coefficient for the vaccine variable in these models, with vaccine effectiveness estimated as (1–HR)×100%. SEs for the coefficients will be used to estimate p values and CIs for the HRs. If a covariate does not satisfy the assumption of proportionality, we will exclude the variable for the multivariable model and will perform the stratified analysis using the covariate.

Detailed methodology for summary and statistical analyses of data collected in this study will be documented in a statistical analysis plan (SAP), which will be dated, filed and maintained by Pfizer. The SAP may modify the plans outlined in the protocol; any major modifications of primary endpoint definitions or their analyses would be reflected in a protocol amendment.

9.8. Quality Control

Only observed data will be used in measuring study variables. It is anticipated that demographic information will be available for nearly all individuals in the study population. All other variables will be defined based on the presence of specific data (eg, diagnosis, procedure, and drug codes) in the analytic file; the absence of such data will be assumed to indicate the absence of the characteristic/event captured by the variable.

9.9. Strengths and Limitations of the Research Methods

Strengths

A significant strength of observational retrospective analyses is that they provide a better understanding of the study population in real world clinical practice as compared to the controlled conditions of a clinical trial.

Limitations

There are several limitations in this study. Given that this is an observational study using health care administrative claims data, residual confounding due to missing or unmeasured information is possible. To examine this, we will assess the effect of meningococcal vaccination on another sexually transmitted disease occuring, at the same age group, as reference disease outcome. If the HRs in any of these models are less than 1.0, it would indicate that residual confounding exists and may result in adjustment of our vaccine effectiveness (VE) estimates.

Second, health care administrative claims data will be available from 01 January 2016 through 31 December 2022. It is possible that some participants may have received a Trumenba vaccination prior to January 1, 2016 or during a period in which we do not have their claims data and be misclassified as unvaccinated with Trumenba. This may underestimate Trumenba vaccine effectiveness because the Men-ACWY-only cohort will include Trumenba vaccinated patients.

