8.1.2. Secondary Objectives

- 1. To examine the effect of at least 2 doses of Trumenba on gonococcal infection in adolescents and young adults of 15-30 years in the US.
- 2. To examine the effect of at least 1 dose of Trumenba on chlamydial infection in adolescents and young adults of 15-30 years in the US.
- 3. To examine the effect of at least 2 doses of Trumenba on chlamydial infection in adolescents and young adults of 15-30 years in the US.

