9.3. Variables

In this study, the variables of interest are age, gender, state of residence, date of vaccination and the date of disease diagnosis.

PFIZER CONFIDENTIAL CT24-WI-GL02-RF02 4.0 Non-Interventional Study Protocol Template For Secondary Data Collection Study 01-Jun-2022 Page 12 of 22

Table 1.Variable List

Variable	Role	Operational Definition
Birth Year	Covariate	Birth year (age to be calculated based on July 1 of birth year)
Gender	Covariate	Male, Female, Unknown
Residence (ZIP code)	Covariate	First 3 digits of the zip code from individuals' most recent enrollment
MenACWY vaccination	Non-exposure	Current procedural terminology (CPT) codes and National Drug Codes (NDC) listed below
Trumemba vaccination	Exposure	CPT and NDCs listed below
Gonococcal infection	Primary Outcome	ICD-10-CM codes listed below
Chlamydial infection	Reference disease Outcome	ICD-10-CM codes listed below

Code	Туре
A540	ICD-10-CM
A5400	ICD-10-CM
A5401	ICD-10-CM
A5402	ICD-10-CM
A5403	ICD-10-CM
A5409	ICD-10-CM
A541	ICD-10-CM
A542	ICD-10-CM
A5421	ICD-10-CM
A5422	ICD-10-CM
A5423	ICD-10-CM
A5424	ICD-10-CM
A5429	ICD-10-CM
A543	ICD-10-CM
A5430	ICD-10-CM
A5431	ICD-10-CM
A5432	ICD-10-CM
A5433	ICD-10-CM
A5439	ICD-10-CM
A544	ICD-10-CM
A5440	ICD-10-CM
A5441	ICD-10-CM
A5442	ICD-10-CM
A5443	ICD-10-CM
A5449	ICD-10-CM
A545	ICD-10-CM
A546	ICD-10-CM
A548	ICD-10-CM
A5481	ICD-10-CM
A5482	ICD-10-CM
A5483	ICD-10-CM
A5484	ICD-10-CM
A5485	ICD-10-CM
A5486	ICD-10-CM
A5489	ICD-10-CM
A549	ICD-10-CM

Table 2. Diagnosis Codes for Identifying Gonococcal Infections

Code	Туре
A55	ICD-10-CM
A560	ICD-10-CM
A5600	ICD-10-CM
A5601	ICD-10-CM
A5602	ICD-10-CM
A5609	ICD-10-CM
A561	ICD-10-CM
A5611	ICD-10-CM
A5619	ICD-10-CM
A562	ICD-10-CM
A563	ICD-10-CM
A564	ICD-10-CM
A568	ICD-10-CM
A71	ICD-10-CM
A710	ICD-10-CM
A711	ICD-10-CM
A719	ICD-10-CM
A74	ICD-10-CM
A740	ICD-10-CM
A748	ICD-10-CM
A7481	ICD-10-CM
A7489	ICD-10-CM
A749	ICD-10-CM

 Table 3.
 Diagnosis Codes for Identifying Chlamydial Infections

Code	Туре	Description
90734	CPT	Menactra/Menveo Vaccination
90619	CPT	Menquadfi Vaccine
49281-0589-05	NDC	Menactra Vaccine
46028-0208-01	NDC	Menveo Vaccine
58160-0955-09	NDC	Menveo Vaccine
49281-0589-58	NDC	Menactra Vaccine
49281-0590-58	NDC	Menquadfi Vaccine
46028-0218-11	NDC	Menveo Vaccine
58160-0958-01	NDC	Menveo Vaccine
58160-0959-01	NDC	Menveo Vaccine
46028-0219-11	NDC	Menveo Vaccine
54569-5687-01	NDC	Menactra Vaccine
50090-1890-01	NDC	Menactra Vaccine
49281-0590-05	NDC	Menquadfi Vaccine

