3 HYPOTHESES AND DECISION RULES

PFIZER CONFIDENTIAL CT24-WI-GL03-RF03 2.0 Non-Interventional Statistical Analysis Plan For Secondary Data Collection Study 01-Jun-2020 Page 6 of 28 This is an exploratory study, thus no hypothesis will be tested. There will be more than 500,000 individuals in which approximately 15% will be the experimental group. Assming a total of 500,000 subjects, and the probability of failure in the experimental group over the maximum time period of the study is 0.0036 and the probability of failure in the control group over the maximum time period of the study is 0.0048. This provides a power of 94% assuming a hazard ratio of 80% (20% vaccine effectiveness) and at an alpha of 0.05. The calculation was made using "powerSurvEPI" package under RStudio (Version 1.1.453).

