7.2.1.1 Primary Endpoint - Main Analysis

Vaccination Status

If a participant received at least one dose of Trumenba and at least one dose of MenACWY vaccine will be considered as vaccinated (exposed population).

Analysis

We will assess gonococcal infection that occurred between 14 days after zero time and till end of the study period. We will censor the data at death date (if known), plan disenrollment, or the end of the study period, whichever comes first. In descriptive analyses, we will fit Kaplan-Meier curves. We will also create unadjusted and covariate adjusted Cox proportional hazard regression models with time varying approach verifying first that the proportionality assumption was satisfied for all independent variables. Since the individuals entered into the surveillance at different points of time, we will employ the computing process algorithm of the proportional hazard model where the date of entry and the date of end of follow-up will be used in the model instead of time contribution to compute the hazard ratios.

Hazard ratios (HRs) will be estimated by exponentiation of the coefficient for the vaccine variable in these models, with vaccine effectiveness estimated as $(1-HR)\times100\%$. Standard errors (SEs) for the coefficients will be used to estimate p-values and 95% CIs for the HRs. If a covariate does not satisfy the assumption of proportionality, we will exclude the variable for the multivariable model and will perform the stratified analysis using the covariate. Both crude and adjusted VE with its corresponding 95% CI will be calculated.

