7.4.2.2 Secondary Endpoint 2 - Effectiveness of trumenba against chlamydial infection

VE calculated as 1 minus the hazard ratio for chlamydial infection between the recipients (aged 15-30 years) of both Trumenba (at least one dose) and MenACWY (at least one dose) vaccines and the recipients (aged 15-30 years) of MenACWY vaccine only multiplied by 100, adjusted for potentially confounding variables.

PFIZER CONFIDENTIAL CT24-WI-GL03-RF03 2.0 Non-Interventional Statistical Analysis Plan For Secondary Data Collection Study 01-Jun-2020 Page 14 of 28

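### Protocol 9.9 reads any chlamydia hazard ratio below 1.0 as residual confounding, with no confidence interval attached and no reading for a ratio above 1.0; the SAP does not replace it

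*Protocol*

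**What the plan says.** Protocol 9.9 concedes that residual confounding is possible and names one check for it: "we will assess the effect of meningococcal vaccination on another sexually transmitted disease occuring, at the same age group, as reference disease outcome". Table 1 in Protocol 9.3 identifies that disease as chlamydial infection, with the role "Reference disease Outcome". The reading of the check is then given in one sentence: "If the HRs in any of these models are less than 1.0, it would indicate that residual confounding exists and may result in adjustment" of the VE estimates.

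The set of models is not defined. Protocol 8.1.2 has at least two for chlamydia: one for at least 1 dose, and one described as "To examine the effect of at least 2 doses of Trumenba on chlamydial infection". The SAP table shells add crude and adjusted versions, chlamydia without co-infection, ages 16-23, and four follow-up windows.

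Intervals are planned. Protocol 9.7 says "SEs for the coefficients will be used to estimate p values and CIs for the HRs", and SAP 7.2.1.1, whose method the chlamydia analyses follow, says "Both crude and adjusted VE with its corresponding 95% CI will be calculated". Neither is linked to the sentence in 9.9.

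The SAP presents chlamydia only as a VE endpoint, under headings such as "Secondary Endpoint 2 - Effectiveness of trumenba against chlamydial infection". It has no rule for reading chlamydia as a check on confounding and no adjustment step.

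**The concern.** Chlamydia is the only stated check for residual confounding in a study whose models adjust for age, sex and US region alone. The sentence in 9.9 has four gaps:

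- It attaches no CI, p value or margin to the threshold of 1.0.
- It covers only HRs below 1.0. Confounding in the other direction, which would hide a real effect, has no stated reading.
- It applies to any of an undefined set of models.
- It allows adjustment of VE without naming a method or a condition.

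An estimate slightly below 1.0 is what chance gives half the time when nothing is wrong. Followed literally, the sentence would often lead to a report of confounding where there is none, would say nothing about confounding that masks VE, and would leave the decision to adjust VE until results are known.

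**Working it through.** **Plan's own figures.** The documents state no error rate for this reading. The SAP section 3 inputs can be checked against its stated power of 94%. Events: 75,000 × 0.0036 + 425,000 × 0.0048 = 270 + 2,040 = 2,310. With k = 75,000/425,000 = 0.1765 and HR 0.80, z = √(k × 2,310) × 0.20/(0.80k + 1) − 1.96 = 1.58, so power is 94.3%. The figure reproduces.

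**Inputs used below.** From SAP section 3: 500,000 subjects, 15% exposed, and "probability of failure in the control group over the maximum time period of the study is 0.0048". That probability is for gonorrhoea. The documents give no chlamydia event rate, so chlamydia events are assumed to be 1 to 4 times the gonorrhoea events. At HR 1.0 and 1 times the events, the exposed cohort has 75,000 × 0.0048 = 360 events and the reference cohort 2,040. The SE of log HR is √(1/360 + 1/2,040) = 0.0572, or 0.0286 with four times the events.

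**One model, true HR 1.0.** The estimated log HR is approximately symmetric about 0, so P(HR < 1.0) = Φ(0) = 50%, whatever the SE. Exact binomial checks with 15% exposed give 50.3%, 49.4% and 49.6% at 2,310, 5,000 and 10,000 events.

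**Two dose models, true HR 1.0.** The cohort with 2 or more doses is nested in the cohort with 1 or more, and both share the reference cohort. If a share f of exposed events falls in recipients of 2 or more doses (f is not in the documents), the correlation of the two log HRs is r = √[(1/360 + 1/2,040)/(1/(360f) + 1/2,040)], and P(at least one HR < 1.0) = 1 − [1/4 + arcsin(r)/(2π)].

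| f | r | P(any HR < 1.0) |
|---|---|---|
| 0.2 | 0.477 | 67.1% |
| 0.5 | 0.735 | 61.9% |
| 0.9 | 0.956 | 54.7% |

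A Poisson simulation gives 67.6%, 62.2% and 55.1%.

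**The unread direction.** Suppose the true chlamydia HR is 1.10 and the same confounding acts on gonorrhoea. A true VE of 20% is then seen as 1 − 0.80 × 1.10 = 12%. The chlamydia estimate falls below 1.0 in 4% of such studies or fewer, and nothing says what an estimate above 1.0 means.

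**Reading the planned CI instead.** At true HR 1.0, the two-sided 95% CI excludes 1.0 in 5% of studies for one model. For other values, exposed events are scaled by the HR (324 at 0.90, 396 at 1.10, before multiplying by 1 to 4):

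| True chlamydia HR | P(HR < 1.0) | P(95% CI excludes 1.0) |
|---|---|---|
| 0.90 | 96% to over 99.9% | 42% to 94% |
| 1.10 | 4% to under 0.1% | 41% to 93% |

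An estimate of exactly 1.0 would have a 95% CI of 0.89-1.12 at 1 times the events and 0.95-1.06 at 4 times.

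**The case against.** Protocol 9.9 does not say that the point estimate alone decides. SAP 3.2 sets a two-sided alpha of 0.05, and CIs and p values are planned, so a reader could take the sentence to mean an HR shown to be below 1.0. On that reading the chance of a false signal for one model is 2.5%. It is a possible reading, but not one the documents make: SAP 3.2 is general and not linked to 9.9, SAP 3 and 3.1 say no hypothesis is tested, and the sentence in 9.9 carries no qualifier.

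The text stands in a limitations section of an exploratory study, and adjustment is only a possibility. That is true and limits the seriousness.

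A true HR of exactly 1.0 is an idealised case with so few covariates, and at 0.90 the literal criterion almost always fires. A low threshold can be a sensible cautious flag. That also stands, but the protocol does not call it a flag: it says the result would indicate that confounding exists.

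Looking for bias that inflates VE is natural in a vaccine cohort. However, Protocol 9.1 speaks of differences in health seeking and risk behaviour without giving a direction. Nor would an HR above 1.0 be hidden, because the SAP shells tabulate chlamydia VE with its 95% CI whatever its sign. What is missing is how to interpret it.

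A reader might also infer that any adjustment could only lower VE, or try to compute by how much. The documents do not support this. No method is named; a ratio correction would lower VE when the chlamydia HR is below 1.0, but added covariates or stratification could move it either way.

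**Conclusion.** The concern holds as a defect in the stated inference. Taken literally, the criterion is met about 50% of the time for one model when the true chlamydia HR is 1.0, independent of sample size. Across the two dose models it is met about 55-67% of the time, which rests on the assumed 90-20% share of exposed events in recipients of 2 or more doses. Confounding that masks VE has no reading; the step from 20% to 12% assumes a bias factor of 1.10 acting equally on both infections.

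It should not be read as a fault in the planned estimates or intervals, which are unaffected. Nor does it show that VE will be wrongly adjusted by some amount: the size and direction of any adjustment cannot be derived from the documents. It should be corrected before analysis because this is the only stated check on confounding and the SAP is silent on how to read it.

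**What to change.** Change the wording of Protocol 9.9 and add the same text to the SAP:

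1. Name chlamydia as a negative-control outcome, read on one adjusted model chosen in advance, for example the model for at least 1 dose with follow-up to the end of the study. Use chlamydial infection only as a sensitivity reading. The choice is debatable: if a gonorrhoea diagnosis prompts testing that finds chlamydia, a real effect on gonorrhoea could lower the HR for all chlamydia.
2. Read the estimate with its planned two-sided 95% CI in both directions. A CI excluding 1.0 on either side is evidence of residual confounding. A CI including 1.0 is reported as the range of bias not ruled out, not as absence of confounding.
3. State that the primary VE is not altered after results are seen. Any adjusted VE is supportive, with its method and assumptions fixed in advance.

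No new data or models are needed. The price is sensitivity to bias that inflates VE: at a true chlamydia HR of 0.90 the CI excludes 1.0 in about 42-94% of studies, against 96% to over 99.9% for the literal criterion, assuming chlamydia events 1 to 4 times gonorrhoea events. Reporting the range of bias not ruled out is there to offset this.

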9.10. Other Aspects

Not applicable.

10. PROTECTION OF HUMAN SUBJECTS

10.1. Patient Information

This study involves data that exist in anonymized structured format and contain no patient personal information.

10.2. Patient Consent

As this study involves anonymized structured data, which according to applicable legal requirements do not contain data subject to privacy laws, obtaining informed consent from patients by Pfizer is not required.

10.3. Institutional Review Board (IRB)/Independent Ethics Committee (IEC)

The study databases will be de-identified prior to their release to study investigators, as set forth in the corresponding Data Use Agreement. The study databases have been evaluated and certified by an independent third party to be compliant with the HIPAA of 1996 statistical de-identification standards and to satisfy the conditions set forth in Sections 164.514 (a)-(b)1ii of the HIPAA Privacy Rule regarding the determination and

PFIZER CONFIDENTIAL CT24-WI-GL02-RF02 4.0 Non-Interventional Study Protocol Template For Secondary Data Collection Study 01-Jun-2022 Page 19 of 22

documentation of statistically de-identified data. Use of the study databases for health services research is therefore fully compliant with the HIPAA Privacy Rule and federal guidance on Public Welfare and the Protection of Human Subjects (45 Code of Federal Regulations [CFR] 46 §46.101) and IRB approval is not required.

10.4. Ethical Conduct of the Study

The study will be conducted in accordance with legal and regulatory requirements, as well as with scientific purpose, value and rigor and follow generally accepted research practices described in Good Pharmacoepidemiology Practices (GPP) issued by the International Society for Pharmacoepidemiology (ISPE), Good Epidemiological Practice (GEP) guidelines issued by the International Epidemiological Association (IEA), Good Outcomes Research Practices issued by the International Society for Pharmacoeconomics and Outcomes Research (ISPOR), International Ethical Guidelines for Epidemiological Research issued by the Council for International Organizations of Medical Sciences (CIOMS), European Medicines Agency (EMA) European Network of Centres for Pharmacoepidemiology and Pharmacoepidemiology, and Food and Drug Administration (FDA) Guidance for Industry: Good Pharmacovigilance and Pharmacoepidemiologic Assessment, and FDA Draft Guidance for Industry and FDA Staff: Best Practices for Conducting and Reporting of Pharmacoepidemiologic Safety Studies Using Electronic Healthcare Data Sets and/or equivalent.

11. MANAGEMENT AND REPORTING OF ADVERSE EVENTS/ADVERSE REACTIONS

This study involves data that exist as structured data by the time of study start.

In these data sources, individual patient data are not retrieved or validated, and it is not possible to link (ie, identify a potential association between) a particular product and medical event for any individual. Thus, the minimum criteria for reporting an adverse event (AE) (ie, identifiable patient, identifiable reporter, a suspect product, and event) cannot be met.

12. PLANS FOR DISSEMINATING AND COMMUNICATING STUDY RESULTS

Formal communication of the results of this research will be done by Pfizer authors through peer-reviewed publications. For all publications relating to the Study, Pfizer will comply with recognized ethical standards concerning publications and authorship, including Section II -"Ethical Considerations in the Conduct and Reporting of Research" of the Uniform Requirements for Manuscripts Submitted to Biomedical Journals, http://www.icmje.org/index.html#authorship, established by the International Committee of Medical Journal Editors.

In the event of any prohibition or restriction imposed (eg, clinical hold) by an applicable competent authority in any area of the world, or if party responsible for collecting data from the participant is aware of any new information which might influence the evaluation of the benefits and risks of a Pfizer product, Pfizer should be informed immediately.

PFIZER CONFIDENTIAL CT24-WI-GL02-RF02 4.0 Non-Interventional Study Protocol Template For Secondary Data Collection Study 01-Jun-2022 Page 20 of 22

15. LIST OF FIGURES

None.

1 AMENDMENTS FROM PREVIOUS VERSION(S)

This is an initial SAP

2 INTRODUCTION

This statistical analysis plan (SAP) provides the detailed methodology for summary and statistical analyses of the data collected in Study B1971066. This document may modify the plans outlined in the protocol; however, any major modifications of the primary endpoint definition or its analysis will also be reflected in a protocol amendment. Note that any text taken directly from the protocol is *italicized*, with exceptions note where it appears.

This study is not a post-authorization safety study (PASS) and is not a commitment to any regulatory authority. This aim of this study is to evaluate the effect of Trumenba (fHbp) vaccine on gonococcal infection among 15-30 years in the United States.

2.1 STUDY DESIGN

This is a retrospective cohort study including individuals 15 to 30 years of age enrolled in a health plan covered by IQVIA PharMetrics® Plus during 1 Jan 2016 to until the latest release of the data (October 2022). The study is to estimate the effect of Trumenba vaccination on the disease of interest, in particular, the gonococcal incidences will be compared between the recipients of Trumenba + MenACWY vaccines and the recipients of MenACWY vaccine.

The exposure cohort will be the individuals who have received at least one dose of Trumenba and at least one dose of MenACWY between 1 January 2016 and 31 December 2021. The non–exposure or reference cohort will be the individuals with no dose of Trumenba but at least one dose of MenACWY vaccine received during the same time period.

PFIZER CONFIDENTIAL CT24-WI-GL03-RF03 2.0 Non-Interventional Statistical Analysis Plan For Secondary Data Collection Study 01-Jun-2020 Page 4 of 28 The date of index vaccination (zero time) for the exposed cohort is the date of the last dose of Trumenba vaccination, after at least one dose of MenACWY. Trumemba and MenAWCY will be identified by Current Procedural Terminology® (CPT) codes and National Drug Codes (NDC) listed in Appendix Tables 4 and 3, respectively. The index date of the unexposed cohort is the first date of MenACWY vaccination. The diseases of interest are gonococcal infection and chlamydia infections occurring at least 14 days after the zero time. International Classification of Diseases, Tenth Revision, Clinical Modification (ICD-10-CM) codes listed in Appendix Table 1 and 2 will identify gonococcal and chlamydia infections, respectively. Only the first episode will be considered as the event in case of repeated infections. Individuals will be followed until the earliest occurrence of the following: outcome, at death date (if known), at plan disenrollment or end of study period.

Study population

This is a retrospective cohort study and the study population are adolescents and young adults approximately 15 to 30 years of age at their date of vaccination (calculated based on birth year) and will be identified from administrative claims during 01 January 2016 and 31 December 2021.

Data source

This source of the data for this study will be the health care administrative claims data obtained from the IQVIA PharMetrics® Plus, which is a longitudinal health plan database of adjudicated medical and pharmacy claims, including patient enrollment data for national and sub-national health plans and self-insured employer groups in the United States. Data contributors to the database are largely commercial health plans. It is representative of the commercially insured US national population for patients under 65 years of age. It contains a longitudinal view of inpatient and outpatient services, prescription and office/outpatient administered drugs, costs, and detailed enrollment information. All data are compliant to the Health Insurance Portability and Accountability Act (HIPAA) to protect patient privacy. The database is used in a variety

PFIZER CONFIDENTIAL

CT24-WI-GL03-RF03 2.0 Non-Interventional Statistical Analysis Plan For Secondary Data Collection Study 01-Jun-2020 Page 5 of 28 of life sciences and commercial effectiveness studies. Over 250 peer reviewed publications have used PharMetrics Plus data. There will be more than 500,000 subjects for conducting this study.

